8.5 Human Biological Samples

Instructions for the collection and handling of biological samples will be provided in the study-specific laboratory manual. Samples should be stored in a secure storage space with adequate measures to protect confidentiality. For further details on Handling of Human Biological Samples are provided in Appendix C.

Samples will be stored for a maximum of 15 years from the date of the issue of the CSR in line with consent and local requirements, after which they will be destroyed/repatriated.

8.5.1 Pharmacokinetics

Pharmacokinetic parameters are not evaluated in this study.

8.5.2 Immunogenicity Assessments

Serum samples for immunogenicity assessments will be collected according to the SoA (Section 1.3). Samples will be collected, labelled, stored, and shipped as detailed in the Laboratory Manual.

8.5.2.1 SARS-CoV-2 Serology Assessments

Serum samples will be collected to assess SARS-CoV-2 antigen-specific antibody levels from all participants according to the SoA (Section 1.3). Authorised laboratories will assess seroresponse to AZD1222 by a validated immunoassay directed at the SARS-CoV-2 S antigen. The rate of asymptomatic SARS-CoV-2 infection in participants receiving AZD1222 versus placebo will be determined by seroresponse to SARS-CoV-2 N by an immunoassay operated by an authorised laboratory. Serologic assessment to S and receptor-binding domain (RBD) antigens will also be assessed quantitatively using a validated multiplexed MSD immunoassay.

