3 OBJECTIVES AND ENDPOINTS

Table 2Objectives and Endpoints

Objectives	Endpoints
Primary (Immunogenicity)	
To assess antibody responses to AZD1222 Spike antigen following 2 IM doses of AZD1222 or placebo.	• The proportion of participants who have a post-treatment seroresponse (≥ 4-fold rise in titres from Day 1 baseline value) to Spike antigen of AZD1222 (MSD serology assay) at Day 57.
Primary (Safety)	
To assess the safety, tolerability, and reactogenicity profile of the candidate vaccine AZD1222.	(a) Occurrence of solicited local reactogenicity signs and symptoms for 7 days following throughout vaccination.
	(b) Occurrence of solicited systemic reactogenicity signs and symptoms for 7 days following throughout vaccination.
	(c) Occurrence of AEs, SAEs and AESIs for 28 days following throughout vaccination.
	(d) Change from baseline for safety laboratory measures.
Secondary (Immunogenicity)	
To assess antibody responses to AZD1222 RBD antigen following 2 IM doses of AZD1222 or placebo.	• The proportion of participants who have a post-treatment seroresponse (≥ 4-fold rise in titres from Day 1 baseline value) to RBD antigen of AZD1222 (MSD serology assay) at Day 57.
 To assess time course of antibody to AZD1222 Spike and RBD antigens of AZD1222 (MSD serology assay) 	GMT and GMFR of immunogenicity against Spike and RBD antigens of AZD1222 (MSD serology assay) at each time point up to Day 365.
To assess the function of nAb against SARS-CoV-2 spike protein	 Proportion of participants who have a post-treatment seroresponse (≥ 4-fold rise in titres from Day 1 baseline value) to AZD1222 as measured by SARS-CoV-2 nAb (wild-type assay or pseudoneutralisation assay) at Day 57.
	GMT and GMFR of immunogenicity against Spike antigen of AZD1222 as measured by SARS-CoV-2 nAb at each time point up to Day 365.
Secondary (Safety)	
To assess the safety of the candidate vaccine AZD1222.	Occurrence of SAEs and AESIs throughout the study duration up to Day 365.

Objectives	Endpoints				
Exploratory (Descriptive efficacy)					
To describe occurrence of symptomatic COVID-19 in recipients of AZD1222 and placebo.	Virologically confirmed (RT-PCR positive) symptomatic cases of COVID-19.				
To describe occurrence of severe COVID-19 and seroresponse to non-Spike SARS-CoV-2 antigens.	(a) Hospital admissions associated with COVID-19.(b) Intensive care unit admissions associated with COVID-19.				

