8.1 Descriptive Efficacy Assessments

Primary and secondary immunogenicity endpoint assessments are described in Section 8.5.2.1 and Section 8.5.2.2, respectively.

In addition, the following occurrences will be described in AZD1222 and placebo recipients:

- Virologically confirmed (RT-PCR positive) symptomatic cases of COVID-19.
- Evaluation of severe COVID-19 in virologically confirmed (RT-PCR positive) symptomatic cases of COVID-19:
 - Hospital admissions associated with COVID-19.
 - Intensive care unit admissions associated with COVID-19.
 - Deaths associated with COVID-19.
- Seroresponse against non-spike (nucleocapsid) SARS-CoV-2 antigens (MSD serology assay); see Section 8.5.2.1 for details.

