9.4.2 Efficacy (Including Immunogenicity)

Unless otherwise specified, all summaries and figures for immunogenicity will be presented by Cohorts C, D, and Subcohorts D1 and D2, and total participants of Cohort C plus Cohort D separately, based on the TVS and FVS for immunogenicity. Exploratory efficacy analysis will be based on TVS and FVS for efficacy.

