9.4.2.3 Exploratory Endpoint(s)

Exploratory analyses will be conducted to describe occurrence of symptomatic COVID-19 in recipients of AZD1222 and placebo and occurrence of severe COVID-19 and seroresponse to non-Spike SARS-CoV-2 antigens. The exploratory efficacy endpoint will be the incidence of the first virologically confirmed (RT-PCR positive) symptomatic cases of COVID-19 post first dose of study intervention, analysed for the TVS, and the incidence of the first virologically confirmed (RT-PCR positive) symptomatic cases of COVID-19 occurring \geq 15 days post second dose of study intervention, analyzed for the FVS for efficacy.

Kaplan-Meier curves will be presented for each cohort in the AZD1222 and placebo treatment group, showing the cumulative incidence of the first case of RT-PCR positive symptomatic COVID-19 post first dose of study intervention or occurring ≥ 15 days post second dose of study intervention, respectively. In addition, descriptive statistics will also be produced.

Similar descriptive analysis will be conducted on the following more severe cases of COVID-19.

- Hospital admissions associated with COVID-19
- Intensive care unit admissions associated with COVID-19
- Deaths associated with COVID-19

 Seroresponse against non-Spike (nucleocapsid) SARS-CoV-2 antigens (MSD serology assay) will also be assessed using a methodology similar to the one described in Section 9.4.2.1.

Full details of these exploratory efficacy analyses will be documented in the SAP.

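### Section 8.5.2.1 equates nucleocapsid (N) seroresponse with asymptomatic infection, although N seroresponse marks infection with or without symptoms

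*Protocol*

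**What the plan says.** Protocol section 8.5.2.1, under the immunogenicity assessments, gives the rule: "The rate of asymptomatic SARS-CoV-2 infection in participants receiving AZD1222 versus placebo will be determined by seroresponse to SARS-CoV-2 N". The sentence goes on to name the type of assay and laboratory. It sets no condition on symptoms or RT-PCR result.

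Elsewhere the same measure goes by its laboratory name only:

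- Section 3, Table 2, places it under the objective "To describe occurrence of severe COVID-19 and seroresponse to non-Spike SARS-CoV-2 antigens". Asymptomatic infection is not a listed objective or endpoint.
- Section 8.1 lists "Seroresponse against non-spike (nucleocapsid) SARS-CoV-2 antigens (MSD serology assay); see Section 8.5.2.1 for details". In the same list, as a separate item, stands "Virologically confirmed (RT-PCR positive) symptomatic cases of COVID-19".
- Section 9.4.2.3 says that N seroresponse "will also be assessed using a methodology similar to the one described in Section 9.4.2.1". That method is a proportion by arm with a Clopper-Pearson interval, and Fisher's exact test by cohort. The section closes: "Full details of these exploratory efficacy analyses will be documented in the SAP".

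On analysis sets, section 9.4.2 says: "Exploratory efficacy analysis will be based on TVS and FVS for efficacy". Under Table 7, the TVS contains everyone who received at least one dose. The FVS for efficacy requires two doses and no RT-PCR-confirmed COVID-19 before the point 15 days after the second dose.

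**The concern.** AZD1222 expresses only the Spike protein (section 2), so a rise in N antibody points to infection and not to vaccination. It carries no information on symptoms. The protocol uses the marker in that way itself: the FVS for immunogenicity (Table 7) drops every participant with an N seroresponse up to Day 57, symptomatic or not. Section 8.5.2.1 then gives the same marker the label asymptomatic.

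Because section 8.1 sends the reader to 8.5.2.1 for details, that label is the only interpretation of the measure in the protocol. A symptomatic, RT-PCR-confirmed participant who seroconverts would be counted once as a symptomatic case and once as an asymptomatic infection. The reported asymptomatic rate would be too high. A vaccine effect on symptomatic disease could also appear, in part, as an effect on asymptomatic infection, which is a different claim.

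**Working it through.** The protocol states no rate, effect or sample size for asymptomatic infection, so there is no figure to reproduce. The check has two parts.

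**1. Does any section remove symptomatic cases from the N measure?**

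| Place | Removes RT-PCR-confirmed symptomatic cases? |
|---|---|
| 8.5.2.1 (rule) | No |
| 8.1 and 9.4.2.3 (measure and analysis) | No; symptomatic cases are a separate endpoint |
| Table 7, TVS | No |
| Table 7, FVS for efficacy | Only those up to 15 days after dose 2 |

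Dose 2 is planned for Day 29, so the FVS exclusion ends at about Day 29 + 15 = Day 44. Serology samples follow at Days 57, 183 and 365 (Table 1). A symptomatic case after about Day 44 that seroconverts therefore stays in both analysis sets.

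**2. What could this do to the numbers?**

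*Level of the rate.* Allocation is 3:1 in 256 participants, so 192 receive AZD1222 and 64 placebo, or 96 and 32 per cohort. One mislabelled placebo case adds 1/64 = 1.6 percentage points overall, or 1/32 = 3.1 points within its cohort. One mislabelled AZD1222 case adds 1/192 = 0.5 points overall.

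*Contrast.* The following inputs are assumptions, because the protocol gives none:

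- s is the share of placebo infections that are symptomatic.
- VEsym and VEasym are the vaccine effects on symptomatic and asymptomatic infection.
- Every symptomatic infection is RT-PCR confirmed, and every infection gives an N seroresponse, equally in both arms.

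Risk ratio if every N seroresponse is counted:

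RR(all N) = s × (1 − VEsym) + (1 − s) × (1 − VEasym)

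Risk ratio for asymptomatic infection alone: RR(asym) = 1 − VEasym

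With VEsym = 0.70:

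| s | VEasym | RR(all N) | RR(asym) |
|---|---|---|---|
| 0.3 | 0 | 0.09 + 0.70 = 0.79 | 1.00 |
| 0.5 | 0 | 0.15 + 0.50 = 0.65 | 1.00 |
| 0.7 | 0 | 0.21 + 0.30 = 0.51 | 1.00 |
| 0.3 | 0.30 | 0.09 + 0.49 = 0.58 | 0.70 |
| 0.7 | 0.30 | 0.21 + 0.21 = 0.42 | 0.70 |
| any | 0.70 | 0.30 | 0.30 |

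The last row is the important limit. When the two vaccine effects are equal, the contrast is unbiased and only the level is wrong. In the placebo arm the level is inflated by 1/(1 − s): 1.4-fold at s = 0.3, 2-fold at 0.5 and 3.3-fold at 0.7.

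*Expected counts.* Take an assumed 5% placebo infection risk with s = 0.5, VEsym = 0.70 and VEasym = 0. Counting every N seroresponse gives 192 × 0.0325 = 6.2 against 64 × 0.05 = 3.2 participants. Counting only asymptomatic infection gives 192 × 0.025 = 4.8 against 64 × 0.025 = 1.6.

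**The case against.** The strongest reply is that no endpoint called asymptomatic infection is analysed. Table 2, section 8.1 and section 9.4.2.3 all name N seroresponse, and a table of N seroresponse by arm is correct under that title. Section 8.5.2.1 describes a laboratory assessment, section 9.4.2.3 leaves full details to the SAP, and cross-classifying N results with RT-PCR cases is ordinary SAP work. This stands in part. It limits the reach of the error and means that the SAP may already handle it. It does not make the sentence right: a SAP that excluded symptomatic cases would be correcting 8.5.2.1, not completing it.

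A reader might infer more: that the protocol orders all N seroresponders to be reported as asymptomatic, and that the vaccine-placebo contrast is therefore distorted. The document does not support that. It does not say that symptom and RT-PCR data are to be ignored; the overlap follows from an unqualified sentence. Bias in the contrast needs unequal vaccine effects, on which the protocol gives nothing. Inflation in both arms needs at least one symptomatic seroconverter in each, which 64 placebo participants do not guarantee.

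It is also fair that the FVS for efficacy already removes early RT-PCR-positive cases, and that with about three expected placebo infections at a 5% risk no risk ratio would be informative under either definition.

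**Conclusion.** The concern holds as a wrong label in section 8.5.2.1, at minor severity. Followed as written, the sentence counts RT-PCR-confirmed symptomatic cases that seroconvert as asymptomatic infections, in the TVS at any time and in the FVS for efficacy after about Day 44. The level of the rate is inflated whenever such a case occurs.

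Bias in the contrast is possible but conditional. The risk ratios of 0.51 to 0.79 against a true 1.00 illustrate one assumed setting (70% effect on symptomatic infection, none on asymptomatic infection, 30-70% of infections symptomatic). They are not estimates for this trial, and the actual size cannot be derived from the protocol.

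The consequence is confined to an exploratory, descriptive measure. No primary or secondary endpoint, hypothesis or sample-size statement uses the asymptomatic rate.

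**What to change.** In section 8.5.2.1, describe N seroresponse as SARS-CoV-2 infection irrespective of symptoms. This agrees with the naming in Table 2, section 8.1 and section 9.4.2.3, and needs no new analysis.

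If an asymptomatic rate is to be reported as well, define it in 8.5.2.1 and 9.4.2.3 as N seroresponse without RT-PCR-confirmed symptomatic COVID-19 up to that serum sample, and show total N seroresponse beside it. State the remaining limitation: under section 4.1.4 symptomatic participants are directed to testing only if necessary, so those never tested by RT-PCR may still be classed as asymptomatic.

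The cost is one reworded sentence and, for the second option, one derived flag. Both data sources are already planned. The second option leaves a smaller asymptomatic count, which the report should present descriptively.

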8.5.2.2 SARS-CoV-2 Neutralising Antibody Assessments

Serum samples to measure SARS-CoV-2 nAb levels will be collected according to the time points specified in the SoA (Section 1.3). Authorised laboratories will measure nAbs to SARS-CoV-2 using validated wild-type neutralisation assay or pseudoneutralisation assays.

8.5.3 Pharmacodynamics

Pharmacodynamics are not evaluated in this study.

8.6 Human Biological Sample Biomarkers

Biomarkers are not evaluated in this study.

8.7 Optional Genomics Initiative Sample

Optional Genomics Initiative research is not applicable in this study.

8.8 Medical Resource Utilisation and Health Economics

Medical resource utilisation and health economics are not applicable in this study.

9 STATISTICAL CONSIDERATIONS

9.1 Statistical Hypotheses

The primary immunogenicity endpoint is the proportion of participants who have a post-treatment seroresponse (≥ 4-fold rise in titres from Day 1 baseline value) to the Spike antigens of AZD1222 (MSD serology assay) at Day 57.

Let p_{active} and p_{placebo} denote the proportion of participants who have a post-treatment seroresponse for the AZD1222 treatment and placebo group, respectively, then the null hypothesis and alternative hypothesis are defined as follows:

- Null hypothesis: $p_{\text{active}} = p_{\text{placebo}}$
- Alternative hypothesis: $p_{\text{active}} \neq p_{\text{placebo}}$

where p is the proportion of seroresponse participants.

The proportion of participants who have a post-treatment seroresponse will be compared between AZD1222 treatment and placebo using the Fisher's exact test at the 2-sided 5% alpha level for each cohort. No adjustment for multiple testing will be made.

9.2 Sample Size Determination

Regarding Cohort C, 128 participants will be randomised in a 3:1 ratio to receive either AZD1222 or placebo. Regarding Cohort D, in a similar way, 128 participants will be randomised in a 3:1 ratio to receive either AZD1222 or placebo, but participants will be

stratified at randomisation by age group (ie Subcohorts D1 vs D2). At least 30% of participants in Cohort D will be secured for participants with age \geq 70 years.

These sample sizes (96 for AZD1222 versus 32 for placebo) were determined mainly for safety evaluation and based on feasibility. With the sample size of 96 participants in the AZD1222 treatment arm in each cohort, at least 1 participant with an AE of incidence rate of 2.5% can be detected with probability of about 90%. The placebo arm is needed for securing the objectivity of the safety evaluation of the AZD1222 arm and it is also needed as a control for evaluating immunogenicity as stated below. For these purposes, the minimum sample size was given to the placebo arm (1/3 of the AZD1222 arm).

It is difficult to calculate an accurate sample size necessary for comparing the proportion of participants who have a seroresponse to SARS-CoV-2 spike protein between the AZD1222 and placebo arms because of insufficient information on immunogenicity in both arms at the moment. It is expected that the minimum number of participants per cohort will be about 36 in the primary analysis. Under a slightly conservative assumption about seroresponse rates of 10% assumed on placebo and over 75% on AZD1222, it is expected that the sample size of 36 (27 for AZD1222 vs 9 for placebo) will provide 93% power for showing the superiority of seroresponse of the AZD1222 treatment compared with placebo based on Fisher's exact test at 2-sided 5% alpha.

9.3 Populations for Analyses

The following populations are defined:

Table 7 Populations for Analysis

Population/Analysis set	Description
All participants analysis set	All participants screened who signed informed consent form for the study, to be used for reporting disposition and screening failures.
Total vaccinated analysis set (TVS)	All participants who have received at least one dose of study intervention. Erroneously vaccinated participants (eg, those randomised to placebo treatment but were actually given active vaccine treatment) are accounted for in this analysis set by assigning them to the treatment they actually received. This analysis set will be used for the analysis of safety, exploratory efficacy and immunogenicity endpoints.

Population/Analysis set	Description
Fully vaccinated analysis set (FVS) for immunogenicity	All participants in the TVS who have received two doses of study intervention and have no important protocol deviations judged to have the potential to interfere with the generation or interpretation of immune responses. Protocol deviations will be reviewed by the study team before unblinding to determine exclusion from the immunogenicity. Participants who have a postbaseline seroresponse (≥ 4-fold rise in titres from Day 1 baseline value) to nucleocapsid antibodies by MSD serology assay at post-baseline up to Day 57 will be excluded from this analysis set. This analysis set will be used for the analysis of immunogenicity endpoints.
Fully vaccinated analysis set (FVS) for efficacy	All participants in the TVS who have received two doses of study intervention, and who remain on-study 15 days after their second dose without having had a prior SARS-CoV-2 reverse transcriptase-polymerase chain reaction (RT-PCR) positive confirmed COVID-19 infection. This analysis set will be used for applicable exploratory endpoints.

FVS = fully vaccinated analysis set; MSD = Meso Scale Discovery; RT-PCR = reverse transcriptase-polymerase chain reaction; SARS-CoV-2 = severe acute respiratory syndrome-coronavirus-2; TVS = total vaccinated analysis set

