1.3 Schedule of Activities

 Table 1
 Schedule of Activities

Study Procedure	Screening		Vaccinations/Follow-up								Details in CSP Section or Appendix		
Visit	V1	V2	V3	V4	V5	V6	V7	V8	V9	V10	V11	V12	
Timeline (days)	-14 to 1	1	4	8	15	29	32	36	43	57	183	365	
Time window (days)			± 1	± 2	± 2	± 2	± 1	± 2	± 2	± 2	± 7	± 30	
Informed consent	X												Section 5.1
Verify eligibility criteria	X	X											Sections 5.1 and 5.2
Demography	X												
Medical and surgical history	X	X											
Prior/concomitant medication	X	X	X	X	X	X	X	X	X	X	X	X	
Vaccination		X				X							
Telephone call			X				X						
Vital signs	X	X		X	X	X		X	X	X	X	X	Section 8.2.2
Complete physical examination	X												Section 8.2.1
Targeted physical examination		X		X	X	X		X	X	X	X	X	Section 8.2.1
Urine pregnancy test (WOCBP only)	X	X (pre- dose)				X (pre- dose)							
AEs		X	X	X	X	X	X	X	X	X			Section 8.3
SAEs	X	X	X	X	X	X	X	X	X	X	X	X	Section 8.3
AESIs		X	X	X	X	X	X	X	X	X	X	X	Section 8.3.8
SARS-CoV-2 infection	X	←											

Study Procedure	Screening		Vaccinations/Follow-up								Details in CSP Section or Appendix		
Visit	V1	V2	V3	V4	V5	V6	V7	V8	V9	V10	V11	V12	
Timeline (days)	-14 to 1	1	4	8	15	29	32	36	43	57	183	365	
Time window (days)			± 1	± 2	± 2	± 2	± 1	± 2	± 2	± 2	± 7	± 30	
e-Diary provided ^a		X				X							
e-Diary collected				X				X					
Clinical safety laboratory assessments	X	X		X		X		X		X			Section 8.2.3
Test for antibody against SARS-CoV-2 antigen (lateral flow type test)	X												Section 5.2
Saliva sample for RT-PCR test: SARS-CoV-2 genome detection	X												Section 5.2
Serum sample for SARS-CoV-2 serology (central test, MSD serology assay)	X	X (pre-dose)			X	X (pre- dose)			X	X	X	X	Section 8.5.2.1
Serum for SARS-CoV-2 nAb assessment (central test)		X (pre- dose)				X (pre- dose)				X	X	X	Section 8.5.2.2

AE = adverse event; AESI = adverse event of special interest; CSP = clinical study protocol; MSD = Meso Scale Discovery; nAb = neutralising antibody; RT-PCR = reverse transcriptase-polymerase chain reaction; SAE = serious adverse event; SARS-CoV-2 = severe acute respiratory syndrome-coronavirus-2; WOCBP = women of childbearing potential

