4.2 Scientific Rationale for Study Design

4.2.1 Rationale for Study Design and Participant Population

The placebo arm is needed for securing the objectivity of the safety evaluation of the AZD1222 arm and it is also needed as a control for evaluating immunogenicity.

The participant population is males and females ≥ 18 years of age who have no seropositivity to SARS-CoV-2 and a negative RT-PCR test for SARS-CoV-2. Inclusion of older participants is based on data that are is being gathered from the ongoing University of Oxford-sponsored studies. Study COV001 enrolled participants 18 to 55 years of age. Study COV002 is pursuing an age-escalation design and it is anticipated that at least 60 participants who are 56 to 69 years of age and 100 participants aged ≥ 70 will have received AZD1222 prior to initiation of this study.

The study will exclude females who are pregnant or breastfeeding and children < 18 years of age. Women who are pregnant or breastfeeding are excluded at this point as nonclinical developmental and reproductive toxicity studies to support vaccinating these individuals have yet to be performed. Additionally, it is planned that children and adolescents will be evaluated for their response to the vaccine once safety and efficacy have been established in older participants.

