5.2 Exclusion Criteria

Participants are excluded from the study if any of the following criteria apply:

Medical Conditions

- 1 Known past laboratory-confirmed SARS-CoV-2 infection.
- 2 Positive SARS-CoV-2 RT-PCR test at screening.

Provided that partner is the sole sexual partner of the woman of childbearing potential study participant and that the vasectomised partner has received medical assessment of the surgical success.

Sexual abstinence is considered a highly effective method only if defined as refraining from heterosexual intercourse during the entire period of the study and if it is the preferred and usual lifestyle of the participant.

- 3 Seropositivity to SARS-CoV-2 at screening.
- 4 Significant infection or other illness, including fever > 37.8°C on the day prior to or day randomisation
- Any confirmed or suspected immunosuppressive or immunodeficient state; asplenia; recurrent severe infections and use of immunosuppressant medication within the past 6 months, except topical steroids or short-term oral steroids (course lasting ≤ 14 days).
- 6 History of allergy to any component of the vaccine
- 7 Any history of anaphylaxis or angioedema.
- 8 Current diagnosis of or treatment for cancer (except basal cell carcinoma of the skin and uterine cervical carcinoma in situ).
- 9 History of serious psychiatric condition likely to affect participation in the study.
- 10 Bleeding disorder (eg, factor deficiency, coagulopathy or platelet disorder), or prior history of significant bleeding or bruising following IM injections or venepuncture.
- 11 Suspected or known current alcohol or drug dependency.
- 12 History of Guillan-Barré syndrome or any other demyelinating condition.
- Any other significant disease, disorder or finding which may significantly increase the risk to the participant because of participation in the study, affect the ability of the participant to participate in the study or impair interpretation of the study data.
- 14 Severe and/or uncontrolled cardiovascular disease, respiratory disease, gastrointestinal disease, liver disease, renal disease, endocrine disorder and neurological illness (mild/moderate well controlled comorbidities are allowed).

Prior/Concomitant Therapy

- 15 Receipt of any vaccine (licensed or investigational) other than the study intervention within 30 days before and after each study vaccination.

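### The immunogenicity set screens out infection only by a 4-fold nucleocapsid rise, so Day 1 MSD positives and RT-PCR-confirmed cases without that rise remain in the estimates

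*Protocol*

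**What the plan says.** Protocol Section 9.3, Table 7, sets three conditions for the FVS for immunogenicity.

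- Two doses were received.
- Participants must "have no important protocol deviations judged to have the potential to interfere with the generation or interpretation of immune responses", as judged by the study team before unblinding.
- Anyone with a rise of at least 4-fold from Day 1 to "nucleocapsid antibodies by MSD serology assay at post-baseline up to Day 57 will be excluded from this analysis set".

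The next row, the FVS for efficacy, takes participants "without having had a prior SARS-CoV-2 reverse transcriptase-polymerase chain reaction (RT-PCR) positive confirmed COVID-19 infection". The immunogenicity row has no such clause, and neither row refers to baseline serostatus.

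At entry, Section 4.2.1 describes a population "who have no seropositivity to SARS-CoV-2 and a negative RT-PCR test for SARS-CoV-2", and Section 5.2 excludes "Seropositivity to SARS-CoV-2 at screening" without naming an assay. The Schedule of Activities (Section 1.3) refers to Section 5.2 for "Test for antibody against SARS-CoV-2 antigen (lateral flow type test"), done at Visit 1 only. The "Serum sample for SARS-CoV-2 serology (central test, MSD serology assay") is drawn at Visit 1, before dosing on Day 1, and on Days 15, 29, 43, 57 and later, but the schedule links it to Section 8.5.2.1, not to eligibility. Section 9.4.2 presents immunogenicity "based on the TVS and FVS for immunogenicity"; the TVS has no infection exclusion.

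**The concern.** The nucleocapsid rule exists to keep natural infection out of the estimate of vaccine response, since AZD1222 carries Spike and not nucleocapsid. It leaves two gaps.

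- **Positive at Day 1.** A participant with a past infection that the lateral flow test missed starts with nucleocapsid antibody already raised. It need not rise 4-fold again, so the participant stays in. A high starting Spike titre also makes the 4-fold Spike endpoint harder to meet. The Day 1 MSD result that would show this is collected, but no rule in the protocol uses it.
- **RT-PCR-confirmed infection between Day 1 and Day 57.** If nucleocapsid does not reach a 4-fold rise at a sampled visit, the participant stays in despite a documented infection. Catching COVID-19 is not a protocol deviation, so the deviation clause does not cover it.

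The two gaps pull in different directions. Day 1 positives tend to lower seroresponse and GMFR. Infections during follow-up raise titres, which is most visible in placebo. They need not cancel. At stake are the seroresponse proportions, GMTs and GMFRs by cohort and subcohort, some of which rest on very few placebo participants.

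**Working it through.** **Inputs.** From Protocol Section 9.2: 27 AZD1222 versus 9 placebo per cohort as the expected minimum in the primary analysis, response rates of 75% and 10%, Fisher's exact test at 2-sided 5%, stated power 93%. The protocol gives no rate of retained infection or of Day 1 positivity, so those rates are assumed below.

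**Step 1: the protocol's own figure.** Power is the sum, over all pairs (x, y) that Fisher's test rejects, of Bin(x; 27, 0.75) × Bin(y; 9, 0.10).

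- Equal-tailed convention (one-sided p ≤ 0.025): 92.9%, which reproduces the stated 93%.
- Usual two-sided p-value (sum of tables no more likely than the observed one): 95.4%.

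The figures below use the second convention unless stated.

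**Step 2: effect on the test.** Let q be the proportion of retained participants affected.

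| Assumption | q | AZD1222 rate | Placebo rate | Power |
|---|---|---|---|---|
| None | 0 | 75% | 10% | 95.4% |
| Infected, placebo only, all respond: 0.10 + 0.90q | 1% | 75% | 10.9% | 94.6% |
| Infected, both arms, all respond: 0.75 + 0.25q and 0.10 + 0.90q | 1% | 75.25% | 10.9% | 94.8% |
| Same, both arms | 5% | 76.25% | 14.5% | 92.2% |
| Day 1 positive, both arms, none respond: 0.75(1 − q) and 0.10(1 − q) | 1% | 74.25% | 9.9% | 95.0% |
| Same, both arms | 5% | 71.25% | 9.5% | 92.6% |

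Under the equal-tailed convention, the placebo-only 1% case goes from 92.9% to 91.7%. The loss is about one point at 1% and about three points at 5% in both arms.

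**Step 3: effect on the estimates.**

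- One placebo participant: 1/9 = 11.1 points. From 1/9 to 2/9 responders, the Clopper-Pearson interval moves from 0.3–48.2% to 2.8–60.0%.
- One vaccinee: 1/27 = 3.7 points.
- GMT: if one of n participants has a titre R times that of the others, the GMT is multiplied by R^(1/n). R is not in the protocol; for an assumed R of 50 to 100, the factor is 50^(1/9) = 1.54 to 100^(1/9) = 1.67 at n = 9, and 50^(1/32) = 1.13 to 100^(1/32) = 1.15 at n = 32, the full placebo arm of a cohort.

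**Step 4: cost of excluding.** Removing one participant per arm (26 versus 8) gives 94.1%. Removing one vaccinee only (26 versus 9) gives 95.4%.

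**The case against.** Several points on the other side carry weight.

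- **Same serum.** Spike and nucleocapsid are both read by MSD on the Day 57 sample. An infection too recent to raise nucleocapsid 4-fold has had little time to raise Spike 4-fold in a placebo recipient. A missing Day 57 sample leaves no Day 57 Spike result to distort, and a missing earlier sample does not remove the Day 57 nucleocapsid reading. A false placebo responder therefore needs discordant antibodies in one serum: possible, but uncommon. This stands, and it makes the RT-PCR gap the smaller of the two.
- **Entry and deviation review.** Section 5.2 names no assay, so an MSD-positive baseline might be raised as a deviation before unblinding. It might, but nothing requires it, and the schedule ties the eligibility check to the lateral flow test. This stands only in part.
- **Different purposes.** The FVS for efficacy needs an RT-PCR rule because it defines who is at risk of a first case. Its absence from the other set is not a contradiction. This stands; the case rests on what the nucleocapsid rule can detect, not on a mismatch between rows.
- **Selective testing.** Under Section 4.1.4, RT-PCR in follow-up depends on symptoms. Excluding on it after randomisation selects on something that vaccination may affect. This stands as a cost of the fix.

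A reader might also infer that the primary comparison is at risk. Fixing one of the 9 placebo participants as a responder does lower power from 95.4% to 86.8%, but that figure presupposes that such a case exists, on top of a 10% placebo rate that already allows for responders from any cause. The protocol offers no rate that would make it likely.

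**Conclusion.** The point holds as a modest gap in how the set is defined. The FVS for immunogenicity cannot recognise participants already nucleocapsid-positive at Day 1, and it ignores documented RT-PCR infection unless nucleocapsid also rises 4-fold. The primary superiority conclusion is not threatened: about one point of power at an assumed 1% and about three points at 5%. The exposure is in the descriptive estimates, at 11 points per placebo participant and 3.7 points per vaccinee at 27 versus 9. Day 1 positives among vaccinees bias seroresponse downwards, which is conservative for superiority but still misdescribes the response.

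This rests on assumed contamination rates, an assumed titre ratio for the GMT illustration, and the expected minimum cohort size. The number affected is unknown and probably small. The wish to describe response in people without prior infection is inferred from Section 4.2.1 and from the nucleocapsid rule itself; the stated objective does not use those words.

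**What to change.** Before unblinding, extend the Table 7 exclusion for the FVS for immunogenicity to:

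- (a) nucleocapsid seropositivity on the Day 1 pre-dose MSD sample, by the assay's validated cut-off; and
- (b) RT-PCR-confirmed SARS-CoV-2 infection between Day 1 and the Day 57 sample.

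Keep the TVS as the unrestricted analysis. Report the number excluded under each rule by arm and cohort, and set the FVS results beside the TVS results, so that any selection through symptom-driven testing under (b) is visible.

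The cost is one sentence in Table 7 plus a reference to the cut-off, which the protocol does not state. No new sampling is needed. The set may lose one or two participants, for the small loss of power shown above.
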